3.2.6 Oxygen treatment, ventilator use and mSOFA score

If a subject requires oxygen supplementation, data will be recorded, including method of oxygen supplementation and maximum daily flow rate. Fraction of inspired oxygen [FiO₂] will be reported or derived.

For subjects on high-flow oxygen therapy, FiO₂ will be entered directly into the OXYGEN eCRF page. For subjects not on high-flow oxygen therapy, the maximum daily flow rate will be entered into the OXYGEN eCRF and FiO₂ will be derived as per the conversion guidelines in Section 9.2. Note that the conversion is different depending on whether the subject is on a mask or nasal cannula.

If a subject requires mechanical ventilation, data will be recorded regarding whether ventilator weaning was attempted. For subjects on mechanical ventilation the following ventilator

settings will be recorded: tidal volume, FiO₂, peak airway pressure over the last 24 hours, plateau pressure, positive end expiratory pressure, and respiratory rate. Predicted body weight will be recorded assessment of tidal volume. The data will be recorded daily, and the worst value of the day will be entered in the eCRF.

For subjects on mechanical ventilation, an arterial blood gas (pH, oxygen, carbon dioxide, oxygen saturation and bicarbonate), if available, will be recorded daily. If more than one value is obtained for the arterial blood gases, the value closest to 08:00 will be used.

Assuming that PAO_2 (the partial pressure of alveolar oxygen) is obtained from the alveolar gas equation: $PAO_2 = (FiO_2 \times (760-47)) - (PaCO_2/0.8)$ then alveolar to arterial (AA) gradient will be calculated as: AA gradient = $PAO_2 - PaO_2$.

For subjects admitted to ICU, the modification Sequential Organ Failure Assessment (mSOFA) score will be calculated. For each of the following routine assessments, the worst value of the day will be recorded in the eCRF: oxygen saturation by pulse oximetry (SpO₂)/FiO₂ (mmHg), platelet count, bilirubin, vasopressor use (μ g/kg/min, mmHg), and creatinine (or urine output). For laboratory values, the last available (if within 48 hours) will be used. On days when laboratory results are unavailable, values will be extrapolated from the previously available values.

3.3 Efficacy Variables

The efficacy of acalabrutinib in subjects with COVID-19 when administered with BSC is a secondary endpoint and will be assessed by following variables:

3.3.1 Alive and free of respiratory failure at Day 14 (Day 28)

For the purpose of this study, respiratory failure is defined based on resource utilization of any of the following modalities:

- Endotracheal intubation and mechanical ventilation
- Oxygen delivered by high-flow nasal cannula (heated, humidified, oxygen delivered via reinforced nasal cannula at flow rates > 20 L/min with fraction of delivered oxygen ≥ 0.5)
- Noninvasive positive pressure ventilation or continuous positive airway pressure
- Extracorporeal membrane oxygenation

Only the subject's survival status and respiratory-failure status on Day 14 will be considered for this endpoint. If they experience respiratory failure after first dosed but recover by Day 14, per the definition above, they will be considered alive and free of respiratory failure at Day 14.

Subjects who are lost to follow up prior to Day 14, thus survival status and respiratory status at Day 14 cannot be assessed, will be included in the denominator of this analysis as though they had died or had a respiratory failure.

Similar analysis will be applied for alive and free of respiratory failure at Day 28.

3.3.2 Percent change from baseline in C-reactive protein

This is defined as the percent change from baseline in C-reactive protein (CRP) at Day 1 to Day 14 and Day 28 after first dose. For this endpoint, baseline is defined as the last observation prior to first dose.

3.3.3 Time to clinical improvement of at least 2 points on a 9-point category ordinal scale, live discharge from hospital, or considered fit for discharge, whichever comes first) through Day 28

[figure not shown]
This is defined as the time (in days) from first dose date to the earliest date at which any of the following **event** criteria are met:

- First demonstrated clinical improvement of at least 2 points (i.e., a decline of two points) on the following 9-point category ordinal scale (CSP Table 8)
- Live discharge from hospital
- The date the subject is considered fit for discharge (a score of 0, 1 or 2 on the ordinal scale)

If a subject does not have an event on or before Day 28 and does not withdraw/become lost to follow up from the study prior to Day 28, the data will be censored at Day 28.

If a subject does not have an event but withdraws from the study/ is lost to follow up prior to Day 28, the data will be censored at the last date known that the subject did not demonstrate any of the three above criteria within 28 days.

If a subject does not have an event and dies before Day 28, they will be censored at Day 28.

3.5 Other Variables

3.5.1 Baseline Characteristics

Baseline characteristics that will be collected or derived are:

- Demographics: Age (years), sex, race and ethnicity
- Subject characteristics: Weight, height and body mass index (BMI), where BMI (kg/m²) = Weight/Height²
- Medical history: Name of past and/or concomitant diseases (verbatim and coded using the MedDRA dictionary version 23.0), start and stop dates
- Relevant surgical history: Surgical procedure (verbatim and coded using the MedDRA dictionary version 23.0)
- Pregnancy status for applicable subjects only: test date and result (positive or negative)
- History of substance abuse: cigarettes (former/current/never), vaping (former/current/never), recreational inhaled drugs (former/current/never), alcohol (former/current/never)
- SARS-CoV-2 infection comorbidities: infection comorbidities prior to admission, subcategory, comorbidity start and stop date
- SARS-CoV-2 infection risk factors/lifestyle events: infection risk factor, infection risk factor start and stop date
- SARS-CoV-2 infection signs and symptoms: infection signs or symptoms, clinical event start and stop date
- Respiratory failure status at baseline (with vs without), defined as the following:
 - \circ Without respiratory failure at baseline: subjects do not require oxygen delivered by high-flow nasal cannula or require oxygen delivered by high-flow nasal cannula with flow rate ≤ 20 L/min and FiO₂ < 0.5
 - With respiratory failure at baseline: subjects require oxygen delivered by highflow nasal cannula with
 - 20 L/min < flow rate <30 L/min and
 - $0.5 < \text{FiO}_2 < 0.6$

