1. STUDY DETAILS

This statistical analysis plan (SAP) contains a more detailed description of the analyses in the clinical study protocol (CSP). This SAP is based on version 1 of the CSP.

This study is being conducted to support the ongoing clinical development of acalabrutinib (CALQUENCE®)¹ in hospitalized COVID-19 patients. Because many COVID-19 patients may be unable to swallow capsules due to respiratory failure (eg, they may require endotracheal intubation for ventilator support and NG tube placement), it is important to have a clinically acceptable method to administer acalabrutinib (capsules) via NG tube. Furthermore, due to the acute illness of COVID-19 patients, many hospitalized patients are placed on high doses of PPIs or continuous H2-receptor antagonists to prevent stress ulcers. This study is designed to determine the PK, and safety and tolerability of acalabrutinib suspension, when coadministered with a PPI, in participants with confirmed SARS-CoV-2 infection requiring hospitalization due to respiratory failure (as defined in the table below) attributable to COVID-19 pneumonia and who have an NG tube in place.

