4.4.1 Alive and free of respiratory failure at Day 14 (and 28)

The first efficacy endpoint is the proportion of subjects who are alive and free of respiratory failure at Day 14, where respiratory failure is defined in Section 3.3.1.

The point estimate and its 90% confidence interval (CI; using Wald method with continuity correction) will be calculated and summarized. The difference in the proportion of subjects who are alive and free of respiratory failure at Day 14 with its 90% Cis will be included in this summary. The number and percentage of subjects who experienced respiratory failure but were free of respiratory failure at Day 14 will also be included in above summary.

For those wo have respiratory failure, summary statistics for the number of respiratory failures that occurred will be summarized.

This efficacy endpoint will also be summarized (point estimate and 90% CI Wald method with continuity correction as above) by the following subgroups:

• age (predefined age categories defined in Section 4.2.3)

- sex
- race
- ethnicity
- comorbidities (present vs absent)
- history of substance abuse (former/current/never)
- Concomitant antiviral use (yes vs no)
- Respiratory failure at baseline (with vs without, defined in Section 4.2.3)

The method for handling subjects that withdraw/ are lost to follow up prior to Day 14 is detailed in Section 3.3.1.

Similar analysis will be conducted for Day 28.

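### SAP 3.5.1 defines baseline respiratory failure by high-flow nasal cannula alone, in conflict with 3.3.1: ventilated subjects are labelled as without failure, and some cannula settings fit neither class

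*SAP*

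**What the plan says.** SAP Section 3.3.1 gives the study's definition of respiratory failure for the Day 14 and Day 28 endpoint. Any one of four modalities qualifies:

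- "Endotracheal intubation and mechanical ventilation"
- HFNC above 20 L/min with FiO2 of at least 0.5, with no upper limit on either
- NIV or CPAP
- ECMO

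Section 3.5.1 sets up a separate two-level variable, "Respiratory failure status at baseline (with vs without), defined as the following". The class without failure has two alternative criteria. One is "Without respiratory failure at baseline: subjects do not require oxygen delivered by high-flow nasal cannula". The other is "or require oxygen delivered by high-flow nasal cannula with flow rate ≤ 20 L/min" together with FiO2 below 0.5. The class with failure has a single modality, "With respiratory failure at baseline: subjects require oxygen delivered by highflow nasal cannula with" two joint limits: "20 L/min < flow rate <30 L/min and" FiO2 between 0.5 and 0.6, all printed as strict inequalities.

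Section 4.4.1 uses this variable as one of eight subgroups for the Day 14 and Day 28 endpoint, each with a point estimate and 90% CI: "Respiratory failure at baseline (with vs without, defined in Section 4.2.3". Section 4.2.3 contains no such definition; it stands in 3.5.1.

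Section 1 describes the population as "requiring hospitalization due to respiratory failure" with an NG tube in place, and names intubation as one reason why dosing by that route is needed.

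**The concern.** The SAP defines one clinical state in two ways, and the two disagree on the most heavily supported subjects. A subject intubated before the first dose and still intubated at Day 14 would be recorded as without respiratory failure at baseline and as in respiratory failure at Day 14, on unchanged support. In the subgroup table this subject would be pooled with subjects on low-flow oxygen or room air.

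The baseline classes also do not cover every subject. A programmer who meets an HFNC subject outside both classes must either leave the status missing or choose a class, and the SAP does not say which. The reference in 4.4.1 does not help, because it points to a section without the definition.

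In a small single-group study, baseline severity is much of what a reader has for interpreting the preliminary efficacy proportion, so the label matters even though no test depends on it.

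**Working it through.** The SAP gives no figure to reproduce here. The check applies both rules literally to the same subjects.

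**Rules**

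- Baseline, without (3.5.1): no HFNC, or HFNC with flow ≤ 20 and FiO2 < 0.5.
- Baseline, with (3.5.1): HFNC with 20 < flow < 30 and 0.5 < FiO2 < 0.6.
- Respiratory failure (3.3.1): invasive ventilation, NIV/CPAP, ECMO, or HFNC with flow > 20 and FiO2 ≥ 0.5.

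**By modality and by example HFNC setting (flow in L/min, FiO2)**

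| Support | Baseline class, 3.5.1 | Status under 3.3.1 |
|---|---|---|
| Invasive ventilation, no HFNC | without | failure |
| NIV/CPAP, no HFNC | without | failure |
| ECMO, no HFNC | without | failure |
| Low-flow oxygen or room air | without | no failure |
| HFNC 15, 0.40 | without | no failure |
| HFNC 15, 0.60 | neither | no failure |
| HFNC 25, 0.40 | neither | no failure |
| HFNC 25, 0.55 | with | failure |
| HFNC 25, 0.80 | neither | failure |
| HFNC 40, 0.55 | neither | failure |

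**How wide the HFNC gap is.** Take a grid of flow 5 to 60 in steps of 1 (56 values) and FiO2 0.21 to 1.00 in steps of 0.01 (80 values), so 56 × 80 = 4480 settings. The grid range is an assumption, and the shares below are of settings, not of patients.

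- Without: flow 5–20 (16 values) × FiO2 0.21–0.49 (29 values) = 464.
- With, as printed: flow 21–29 (9) × FiO2 0.51–0.59 (9) = 81.
- Neither: 4480 − 464 − 81 = 3935 (87.8%).
- Failure under 3.3.1: flow 21–60 (40) × FiO2 0.50–1.00 (51) = 2040. Of these, 2040 − 81 = 1959 (96.0%) have no baseline class.

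**Could lost ≤ signs explain it?** With inclusive limits (flow ≤ 30, 0.5 ≤ FiO2 ≤ 0.6), the class with failure has 10 × 11 = 110 settings. Neither becomes 4480 − 464 − 110 = 3906 (87.2%), and 2040 − 110 = 1930 of 2040 (94.6%) failure settings stay unclassified. Inclusive limits do rescue FiO2 of exactly 0.5 at flows above 20 and up to 30, so that single gap should not be pressed.

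**Could an entry cap explain it?** Suppose that enrolment stops at 30 L/min and FiO2 0.6, and the limits are inclusive. The grid shrinks to 26 × 40 = 1040 settings. All 110 failure settings are then classed as with failure. The unclassified ones are flow ≤ 20 with FiO2 ≥ 0.5 (16 × 11 = 176) and flow > 20 with FiO2 < 0.5 (10 × 29 = 290), together 466 of 1040 (44.8%). Under 3.3.1 none of these 466 is respiratory failure. So a cap would remove the most serious HFNC gap and leave the mixed settings without a class.

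**After the fix.** The 3.3.1 rule at baseline, with every other subject as without, leaves no setting unclassified and places ventilation, NIV/CPAP and ECMO in the class with failure.

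**The case against.** The strongest reply is that the SAP may be describing a narrower cohort than its wording suggests. Eligibility sits in the protocol, which was not available for this check. The limits of 30 L/min and FiO2 0.6 look like an entry cap, and ventilated subjects might be excluded. Section 1 also refers to a table defining respiratory failure that does not appear in the text at hand, and the numbering jumps from 3.3 to 3.5, so some text is absent near the definition. Part of this stands: the gaps at or above 30 L/min and FiO2 0.6 may contain nobody. It does not clear the mixed HFNC settings. Exclusion of ventilated subjects also sits badly with Section 1, which cites intubation as a reason for NG dosing, and with Section 3.2.6, which plans daily ventilator settings and blood gases.

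The second reply is that little depends on the variable. It is one baseline line and one of eight subgroups of a secondary endpoint, and Section 4.4 rules out p-values for efficacy. The Day 14 and Day 28 status itself uses 3.3.1. Section 4.5.6 also reports oxygen and ventilation use at each timepoint, so a reader can see the actual level of support. All of this stands and limits the severity.

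Two stronger readings are tempting. A reader might infer that most of the roughly 20 participants would be in the wrong class; the SAP gives no expected mix of support, so no such count can be derived. A reader might also infer that the subgroup comparison would reverse direction. Nothing in the SAP shows that. With so narrow a class, a nearly empty group with failure and several unclassified subjects is at least as plausible.

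**Conclusion.** The conflict between 3.5.1 and 3.3.1 is real as written. Subjects on invasive ventilation, NIV/CPAP or ECMO who do not also require HFNC are labelled without respiratory failure. HFNC subjects with mixed settings have no class under either the printed or the inclusive limits. HFNC subjects at or above 30 L/min or FiO2 0.6 also lack one if they are enrolled, apart from those exactly on a limit if it was meant to be inclusive. The reference in 4.4.1 to Section 4.2.3 is wrong.

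The number of subjects affected cannot be fixed from the SAP: it lies between 0 and about 20, depending on eligibility and on the support given before the first dose. The damage is confined to the baseline table and one descriptive subgroup. The primary PK and safety endpoints, the analysis sets and the overall Day 14 and Day 28 proportions do not use this variable. This is a should-fix matter.

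**What to change.** Rewrite the baseline definition in 3.5.1 so that it applies the 3.3.1 modalities and cut-offs to the last oxygen or ventilator record before the first dose, with every other subject classed as without respiratory failure. Each subject then falls in exactly one class, and baseline and Day 14/28 status share one definition. Correct the reference in 4.4.1 from Section 4.2.3 to Section 3.5.1.

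If almost everyone then falls in the class with failure, report the subgroup as it stands. Do not replace it by another grouping because of the observed split. If a breakdown by level of support is wanted, specify it now as a descriptive baseline tabulation.

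The cost is a few lines of SAP text and one derivation, on the same oxygen and ventilator data that the Day 14 and Day 28 endpoint already needs. No new data are collected and no treatment rule changes. It should be done before programming starts.

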3.5.2 Prior and Concomitant Medications and Procedures

All therapies (drug and non-drug), including herbal preparations, whether prescribed or over-the-counter, that are used during the study will be recorded on the eCRF. Details include generic and/or brand names of the medications, World Health Organisation Drug Dictionary (WHO-DD) encoding (B3 format), reason for use, route, dose, dosing frequency, and start and end dates. Procedures performed during the study will be recorded on the eCRF and details include the procedure name, WHO-DD encoding (B3 format), reason for the procedure, and start and end dates.

Prior therapies are defined as those taken prior to study treatment with a stop date prior to the first dose of study treatment. Concomitant therapies and procedures are defined as those with a stop date on or after the first dose date of study treatment.

Missing start and stop dates for medications and procedures will be handled using the rules described in Section 4.1.

Medications received prior to or concomitantly will be coded using the WHO Drug Dictionary Anatomical Therapeutic Chemical (ATC) classification codes. Concomitant medications will be summarized for the SAS by ATC classification codes. Subjects with the same concomitant medication/procedure multiple times will be counted once per medication/procedure. A medication/procedure that can be classified into more than one chemical and/or therapeutic subgroup will be presented in each subgroup.

4. ANALYSIS METHODS

4.1 General Principles

All statistical analyses will be performed by AZ statistical programming group. Any deviations from the analyses presented in this SAP will be detailed in the clinical study report. All outputs will be produced using SAS® version 9.4 or a later version in accordance with AZ standards.

The below mentioned general principles will be followed throughout the study:

- Demography, baseline characteristics and safety data will be summarised using the SAS. All efficacy data will be summarised and analysed using the EES, unless otherwise specified. PK data will be summarized using the PKS. Exploratory
- Continuous variables will be summarised by the number of observations (n), mean, standard deviation (SD), median, minimum and maximum and will be based on non-missing observations. The minimum and maximum will be reported to the same

number of decimal places as the raw data recorded in the database. The mean and median will be reported to one more decimal place than the raw data. The SD will be reported to two more decimal places than the raw data.

- Categorical variables will be summarized by frequency counts and percentages and include the number of subjects with present data and the number of subjects with missing (not present) data. Percentages will be presented to one decimal place.
- For the PK summaries the reported results will be summarized using appropriate significant figures rather than decimal places.
- Baseline will be the last assessment of the variable under consideration prior to the intake of the first dose of study drug.
- For all summaries, change from baseline variables will be calculated as the post-baseline value minus the value at baseline. The percentage change from baseline will be calculated as ((post-baseline value baseline value)/baseline value) × 100.
- Visit windows will apply as follows:
 - Days 1-14 or discharge: no visit window. Note: if a subject is discharged prior to Day 14 they will visit the site for an assessment 2 to 4 days after discharge. Assessments should match those for Day 14.
 - o Day 20: ± 3 days
 - o Day 28: ± 3 days
 - o Safety follow-up at 28 days after last dose of acalabrutinib: ±3 days
 - Observations recorded on the date closest to the scheduled assessment day (as long as this is within the visit window) will be used as the scheduled assessment. Any observations recorded outside of the visit window will be considered unscheduled visit observations and will not be included in visit-based summaries at a treatment-group level. If multiple observations are recorded per day for ventilator use, the observations closest to 08:00 will be used as the scheduled assessment. If multiple observations are recorded per day for other assessments, the worst assessment reported will be used as the scheduled assessment.
 - For summaries at a subject level, all values will be included (regardless of whether they appear in a corresponding visit-based summary) when deriving a patient level statistic such as a maximum.

No imputation of values for missing data will be performed except for missing or partial start and end dates for AEs and concomitant medication (CM) (Section 9.3). If the data cut-off/snapshot date or the subject's date of death is prior to the date imputed based on the rules outlined in Section 9.3, then the earliest of these dates will be imputed.

4.2 Analysis Methods for Disposition, Demographic, Baseline Characteristics, Prior and Concomitant Medications/Procedures

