1.1 Study Objectives

The objectives for this study and the corresponding endpoints/variables are shown in Table 1.

Table 1 Objectives and Endpoints

Objective	Endpoint/Variable	
Primary Objectives	Primary Endpoints/Variables	
To characterize the PK of acalabrutinib and its active metabolite (ACP-5862) following administration of acalabrutinib suspension, when coadministered with a PPI, in participants with COVID-19	Primary PK parameters for acalabrutinib and ACP-5862 include AUC _{12h} , AUC _{last} , and C _{max} . Additional PK parameters are described in the protocol.	
To assess the safety and tolerability of acalabrutinib suspension in participants with COVID-19 when administered in the presence of PPIs and BSC	Type, frequency, severity, and relationship to study intervention of any treatment-emergent AEs or abnormalities of laboratory tests, SAEs, or AEs leading to discontinuation of study intervention	

¹ CALQUENCE sis a trademark of the AstraZeneca group of companies.

Objective	Endpoint/Variable
Secondary Objective	Secondary Endpoints/Variables
To evaluate the preliminary efficacy of adding acalabrutinib suspension to BSC for treatment of participants with COVID-19	 Proportion of participants alive and free of respiratory failure at Days 14 and 28 Percent change from baseline in CRP (time frame: baseline, Days 3, 5, 7, 14, 28) Time to improvement defined as time to clinical improvement of ≥ 2 points (from first dose date) on a 9-point category ordinal scale, live discharge from the hospital, or considered fit for discharge (a score of 0, 1, or 2 on the ordinal scale), whichever comes first, by Day 28
Exploratory Objectives	Exploratory Endpoints/Variables

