3.2.3 Laboratory assessments

Laboratory tests will be performed as specified in the SoA in the CSP.

For the derivation of baseline and post-baseline visit values, the rules described in Section 4.1 considering definition of baseline, and how to handle multiple records will be used.

Change or percentage change from baseline in hematology and clinical chemistry variables, as well as ferritin and CRP will be calculated for each post-baseline assessment recorded in the eCRF.

Laboratory abnormalities will be defined based on laboratory normal ranges (universal normal ranges for central laboratory tests), and absolute values will be classified as low (below range), normal (within range or limits of range), or high (above range).

Laboratory parameters will also be classified using the National Cancer Institute Common Terminology Criteria (CTC) version 5.0 into CTC grades.

The denominator used in laboratory abnormality summaries will include only evaluable subjects (i.e., those who had sufficient data to have the possibility of an abnormality). Physical examinations and chest imaging, electrocardiograms and echocardiograms

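### On days with more than one record, post-baseline CRP and laboratory values are the worst of the day while baseline is the single last pre-dose value, so change from baseline on those days leans toward worsening

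*SAP*

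**What the plan says.** - **Baseline, general (SAP 4.1).** "Baseline will be the last assessment of the variable under consideration prior to the intake of the first dose of study drug".
- **Baseline, CRP (SAP 3.3.2).** "For this endpoint, baseline is defined as the last observation prior to first dose".
- **Several records on one day (SAP 4.1).** "If multiple observations are recorded per day for other assessments, the worst assessment reported will be used as the scheduled assessment". Ventilator observations are excepted in the same bullet and use the record nearest 08:00. Sections 3.2.5 and 3.2.6 use the same 08:00 rule for vital signs and arterial blood gases.
- **Link to laboratory data (SAP 3.2.3).** For baseline and post-baseline visit values, "the rules described in Section 4.1 considering definition of baseline, and how to handle multiple records will be used". The section names ferritin and CRP among the variables for which change is calculated.
- **Change (SAP 4.1).** "change from baseline variables will be calculated as the post-baseline value minus the value at baseline", with percentage change formed by dividing by baseline.
- **Endpoint (SAP 1.1, Table 1).** Percent change in CRP is a secondary efficacy endpoint at Days 3, 5, 7, 14 and 28.
- **Unscheduled results (SAP 4.5.3).** Unscheduled laboratory results stay out of by-visit summaries but enter out-of-range and worst post-baseline shift tables.

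**The concern.** Two selection rules meet in one subtraction. Baseline is chosen by its timing. Post-baseline, on a day with several records, is chosen by its value. The worst of several readings is on average worse than any one of them, so a subject whose true level has not moved is expected to show a worsening on such a day.

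For CRP, where higher is worse, a real fall looks smaller. The same applies to the other tests in Section 4.5.3 that are adverse in one direction only. For a test that Section 3.2.3 can class as abnormal on either side, the SAP does not say which value is the worst, so neither the programming nor the sign of the shift is fixed.

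The study has one treatment and no comparator, so no control group carries the same shift and lets it cancel. The CRP result is read as an absolute change.

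**Working it through.** The SAP gives no figure on this point, so there is nothing of its own to reproduce. The check has two parts.

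**1. Do the rules differ as written?**

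| Side | Rule | Source |
|---|---|---|
| Baseline | last pre-dose record | 4.1; repeated for CRP in 3.3.2 |
| Post-baseline, one record that day | that record | 4.1 |
| Post-baseline, several records that day | worst record | 4.1 |

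Section 3.2.3 sends laboratory values to Section 4.1 for both baseline and multiple records. With one record a day the two sides match. With several they do not.

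**2. How large is the shift on a repeat day?**

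Assumptions, none of them in the SAP: readings within a day are independent and lognormal with log-scale SD *s* of 0.10 to 0.30 (roughly 10–30% variation); *k* is 1, 2 or 3 records; there is no true change within the day.

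Ratio of the mean of the worst of *k* to the mean of one reading:

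R(k, s) = k × E[Φ(Z + s)^(k−1)], with Z standard normal. For k = 1, R = 1. For k = 2 this reduces to R = 2Φ(s/√2).

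Example: s = 0.20, k = 2 gives 2Φ(0.1414) = 1.1125.

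| s | k = 1 | k = 2 | k = 3 |
|---|---|---|---|
| 0.10 | 1.000 | 1.056 | 1.086 |
| 0.20 | 1.000 | 1.113 | 1.174 |
| 0.30 | 1.000 | 1.168 | 1.264 |

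If every subject-day has repeats, the post-baseline mean is raised by about 6–17% (two records) or 9–26% (three records).

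**Effect on a real fall.** A true 50% fall reads as 1 − 0.5 × R:
- s = 0.10, k = 2: 1 − 0.5 × 1.056 = 0.472, a 47% fall.
- s = 0.20, k = 2: 1 − 0.5 × 1.113 = 0.444, a 44% fall.
- s = 0.30, k = 3: 1 − 0.5 × 1.264 = 0.368, a 37% fall. This is the top of the range.

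**Only some days repeated.** The shift scales with the share of subject-days that have repeats. In a simulation of 1,000,000 draws with no true change, a coefficient of variation of 20% and two records, mean percent change was 15.6% under the plan's rules and 4.0% with the last value on both sides. The excess is 15.6 − 4.0 = 11.6 points:
- all days repeated: 11.6 points
- half: 0.50 × 11.6 = 5.8 points
- a quarter: 0.25 × 11.6 = 2.9 points

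The 4.0% that remains comes from dividing by a noisy baseline, not from the worst-value rule. In the same run the median change was about 12% under the plan's rules and about 0% with last against last.

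**The case against.** **The rule is conditional.** It acts only when a day has several records. A reader might infer that every change from baseline is biased by construction. The text does not support that: with one record a day the shift is exactly zero. This stands.

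**Repeats are not shown to be common.** Table 1 lists CRP on five post-baseline days, and nothing in the SAP says that any laboratory test is drawn more than once a day. A reader might also infer that sicker subjects are sampled more often, so that the bias grows with severity. That is plausible in hospital, but no passage says it. Both limits stand. The multiple-record rule shows only that the authors foresaw repeats.

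**Section 4.5.3 may remove the repeats.** If an extra same-day sample is an unscheduled result, it never reaches the by-visit summaries. This stands in part. Section 4.1 ties the term only to observations outside the visit window, and a second sample on the visit day lies inside it. Two programmers could reasonably differ.

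**A symmetric reading is arguable.** Section 3.2.3 applies the multiple-record rule to baseline values as well. But both baseline definitions say last, and Section 3.3.2 says so for CRP specifically, so the asymmetric reading is the natural one.

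**The consequence is limited.** Section 4.4 rules out p-values for efficacy, the CRP shift works against the drug, and Section 3.2 defines the laboratory part of the safety endpoint by abnormalities rather than mean change. All of this stands and limits the weight of the point.

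**Conclusion.** The asymmetry is in the text and should be corrected. On a post-baseline day with more than one record, percent change in CRP is shifted toward worsening and a fall is understated. By-visit change in other one-directional laboratory tests is shifted the same way. For two-directional tests no sign can be given, because the worst value is undefined.

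Under the stated assumptions the shift runs from zero (one record a day), through about 3 points (20% variation, two records, a quarter of days repeated), to about 26% of the post-baseline mean (log-scale SD 0.30, three records, every day repeated). Where the trial would fall in that range cannot be told from the SAP. Correlation between same-day readings would make the shift smaller.

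It would be tempting to conclude that the efficacy or primary safety findings are invalid. The document does not support that. The summaries are descriptive, no test or power figure depends on them, and the rule cannot create a false CRP benefit through its post-baseline selection. What is lost is an accurate size of change in a single-arm study where that size is the result.

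**What to change.** In Section 4.1, for by-visit change-from-baseline summaries of CRP and laboratory values:

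1. Replace the worst record of the day with a rule that does not depend on the value. The simplest is to keep the last pre-dose value as baseline and use the last record of the day post-baseline. The alternative is the record closest to 08:00 on both sides, as already used for vital signs, blood gases and ventilator data. That option must be restricted to pre-dose samples at baseline, and the baseline definitions in Sections 3.3.2 and 4.1 would need to change with it.
2. Keep worst values for the shift and out-of-range tables in Section 4.5.3, and define the direction for each test where the term is kept.
3. State whether an extra sample on a visit day counts as unscheduled.

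The cost is a few sentences and a small programming change, with no new data. The downside is that by-visit means no longer show the day's worst value. It stays visible in the by-subject listings and in the shift tables. Section 4.5.3 makes the shift tables optional, so the sponsor should confirm that they will be produced for the tests concerned.
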